5.2.4. Dietary Requirements

Valganciclovir absorption is affected by food. Therefore, patients should be instructed to take both valganciclovir and VRx-3996 with food.

In an effort to standardize food intake for the PK assessments, patients will be asked to consume one can of Ensure® or equivalent prior to the dose of study drugs on days with pre- and post-dose PK assessments as outlined in [Section 6.4.1](#). Note that valganciclovir and VRx-3996 should be taken at the same time, including on Cycle 1 Day 1. An Ensure equivalent is defined as any liquid nutrition that is at least 8 ounces in size containing at least 8 grams of protein and at least 6 grams of fat. Alternatively, patients may consume a light breakfast in place of consuming an Ensure equivalent.

Patients are free to determine what food to take prior to all subsequent study drug administrations. On study visit days requiring PK trough levels, patients should be instructed to bring food to consume prior to dosing in order to avoid taking study drugs on an empty stomach and reduce disruption in their dosing schedule.

5.2.5. Dose Adjustments/Modifications/Delays

Dose adjustments for valganciclovir will be made in concert with adjustments to VRx-3996. See [Section 5.1.8](#) for specific details.

For patients with renal impairment, dose adjustments for valganciclovir will be made in accordance with valganciclovir prescribing guidelines as outlined in [Table 13](#).

5.2.6. Drug Interactions

The drug-drug interactions for valganciclovir are those seen with ganciclovir. Drug-drug interaction studies with ganciclovir were conducted in patients with normal renal function. Therefore, with concomitant administration of valganciclovir and other renally excreted drugs, patients with impaired renal function may have increased concentrations of ganciclovir and/or the co-administered drug. Such patients should be closely monitored for toxicity of ganciclovir and the co-administered drug. Established and other potentially significant drug interactions conducted with ganciclovir are listed in [Table 17](#) in the Appendix.

In patients that are receiving a concomitant medication considered to pose a significant drug interaction with valganciclovir, additional monitoring should be conducted as outlined in [Table 17](#).

5.3. Missed Doses

If a scheduled dose of VRx-3996 or valganciclovir is missed, the patient should take the missed dose(s) as soon as possible during the same day, but within 8 hours of the missed dose. If more than 8 hours or an entire day has passed, the normal dosing schedule will be resumed the following day without a change in the daily dose or schedule.

5.4. Vomited Doses

If a scheduled dose of VRx-3996 or valganciclovir is vomited, the patient should contact the site for consideration of anti-nausea medication and dosing should resume with the next scheduled dose. No replacement dose should be given.

5.5. Assessment of Study Drug Compliance

Patient compliance with study drugs will be assessed during study participation. The specific method used to assess study drug compliance may include paper diaries or an automated phone-based system to collect study drugs capsule/tablet counts. Details on the specific method used will be included in the Study Manual.

5.6. Study Drug Accountability

The Investigator or their representative will account for all study drugs supplied by the Sponsor. The Investigator shall maintain adequate records of the disposition of study drug, including dates, quantity, and use by patients. Upon completion of the study, all remaining study drugs will be accounted for and returned to the Sponsor via a traceable method (UPS, FedEx, Marken, etc.) or disposed following the institution's Standard Operating Procedures (SOPs), if instructed by the Sponsor.

6. STUDY PROCEDURES AND SCHEDULE

6.1. Informed Consent

Written informed consent (ICF) in a language fully comprehensible to the prospective patient will be obtained from each patient prior to performing any study-related procedures. A copy of the signed ICF will be provided to the patient. The study site will retain all original versions of signed ICFs.

6.2. Patient Registration

Clinical sites will submit Patient Registration materials through an electronic system for Medical Monitor approval prior to the initial administration of study drugs. Details on the specific electronic system and procedures will be included in the Study and Pharmacy Manuals.

Administration of study drugs should begin within 14 days of approval by the Sponsor (or designee).

6.3. Study Specific Procedures

Study procedures will follow those outlined in the Schedule of Events in [Table 15](#).

6.3.1. End of Treatment Visit

The End of Treatment (ET) Visit is the visit at which the decision is made to discontinue administration of VRx-3996.

If the decision is made to discontinue administration of VRx-3996 outside of a scheduled visit, an attempt will be made to have the patient return for an ET visit.

6.3.2. Safety Follow-Up Visit

Safety will be assessed at the Safety Follow-Up Visit, approximately 28 days following the final administration of VRx-3996/valganciclovir.

6.3.3. Survival and Follow-up Assessment

Survival and follow-up assessment will be conducted at least every 3 months for assessment of additional therapy, response status, and survival following the safety follow-up assessment.

This assessment may be conducted by review of the patient records or by patient contact (e.g., telephone, email). Patients who are unable to be contacted following at least 3 attempts (one of which is contact by registered mail) will be considered lost to follow-up.

6.3.4. Unscheduled Visit

Unscheduled visits will be recorded in the database. The specific tests and evaluations performed during an unscheduled visit will be determined by the Investigator.

6.4. Clinical Laboratory Evaluations

Clinical laboratory evaluations will follow those outlined in the Schedule of Events in [Table 15](#).

Clinical laboratory evaluations will be performed using a central laboratory or a local laboratory. In addition, the clinical sites will provide archived or fresh tissue samples at baseline and in the event of a relapse, if diagnostic biopsies are performed.

6.4.1. Pharmacokinetics

Phase 1b/2 and Tablet Cohorts

A PK assessment of both VRx-3996 and valganciclovir will be performed following the first administration of VRx-3996/valganciclovir in all patients. The scheduled timepoints are shown in [Table 14](#).

Table 14: Pharmacokinetic Sampling and ECG Schedule for Valganciclovir and VRx-3996

Time	Administration	PK Sampling and ECG Schedule		
Cycle 1 & 2, Day 1		Plasma	ECG	Urine (Cycle 1 only)
Pre-dose***	Meal supplement*	X	X (triplicate)	Void
0 hour	Valganciclovir and VRx-3996			N/A
0.5 hour (± 15 min)		X	X (triplicate)	0–3 hr collection
1 hour (± 15 min)		X	X (triplicate)	
2 hour (± 15 min)		X	X (triplicate)	
4 hour (± 15 min)		X	X (triplicate)	3–8 hr collection
6 hour (± 15 min)		X	X (triplicate)	
8 hour (± 30 min)		X		
Cycle 1 Day 2**				
Pre-dose***	Meal supplement*	X	X (triplicate)	N/A
0 hour	Valganciclovir and VRx-3996			N/A
2 hour (± 15 min)		X	X (triplicate)	N/A
Cycle 1 & 2, Day 15**				
Pre-dose***	Meal supplement*	X	X (triplicate)	N/A
0 hour	Valganciclovir and VRx-3996			N/A
2 hour (± 15 min)		X	X (triplicate)	N/A

* Ensure or equivalent should be consumed prior to dosing. Alternatively, patients may consume a light breakfast in place of consuming an Ensure or equivalent.

** Patients should be reminded not to take their dose at home prior to coming into the clinic on these days. Study visits with PK assessments should occur on days that the patient will take both study drugs, VRx-3996 and valganciclovir.

*** Pre-dose ECG should be conducted prior to meal supplement. If possible, patients should not consume additional food between dose and last ECG timepoint. If 6 hr fasting time for ECGs is not feasible for patients, a high protein, low carb snack immediately following an ECG to maximize the time between food and the next ECG.

At selected sites, urine will be collected for levels of VRx-3996 and its metabolites Cycle 1 Day 1. Patients will be instructed to void urine prior to administration of study drug, then all urine will be collected between 0 and 3 hours, and 3 and 8 hours. Detailed instructions are included in the Study Manual.

Pharmacokinetic analysis will be performed at a central laboratory designated by the Sponsor.

Instructions on the collection, processing, and shipment of patient PK samples for these assays will be provided in the Laboratory Manual.

If available, back-up PK aliquots may be used for future assessment of VRx-3996 metabolites (if identified).

6.4.2. Exploratory Biomarkers

Exploratory biomarkers will be evaluated in this study as indicated in [Table 15](#). Archived blood, PBMCs, plasma, and/or tissue samples may be used for assessment of other exploratory biomarkers (if identified).

Details on the collection procedure and timing for each exploratory biomarker will be provided in the Study Manual.

7. SCHEDULE OF EVENTS

The study procedures for the Phase 1b and Phase 2 portions of the study will follow those outlined in [Table 15](#).

Table 15: Schedule of Events

Cycle	SR	1					2		3+		ET	ST	SV
Cycle Day		1	2	8	15	22	1	15	1	15			
Assessment													
Informed consent	X												
Medical history (includes donor data)	X												
EBER/histology sample	X						[X]		[X]		[X]		
Height	X												
Physical examination	X												
Symptom-directed exam		X	X	X	X	X	X	X	X	X	X	X	
Vital signs	X	X	X	X	X	X	X	X	X	X	X	X	
Performance status	X	X	X	X	X	X	X	X	X	X	X	X	
Adverse events		X	X	X	X	X	X	X	X	X	X	X	
Concomitant medications	X	X	X	X	X	X	X	X	X	X	X	X	
Urinalysis	X	X		X	X	X	X	X	X	X	X	X	
Hematology	X	X	X	X	X	X	X	X	X	X	X	X	
Chemistry	X	X	X	X	X	X	X	X	X	X	X	X	
Coagulation	X	X		X	X	X	X	X	X	X	X	X	
Serum pregnancy test	X												
Urine pregnancy test		X					X		X				
12-lead ECG	X	X	X	X	X	X	X	X	X	X	X	X	
Head CT/MRI	X												
Disease assessment	X								X		X		
PK sample(s)		X	X		X		X	X					
Urine PK sample collection		X											
Hepatitis B antigen/antibodies	X												
Hepatitis B DNA PCR	X												
Hepatitis C antibodies	X												
Hepatitis C qPCR	X												

Cycle	SR	1				2		3+		ET	ST	SV
HLA testing		X										
Exploratory Biomarkers												
-Histone H3 acetylation		X	X	X			X					
-Immune profile		X			X		X		X		X	
-EBV and CMV qPCR		X	X	X	X	X	X		X			
VRx-3996/valganciclovir distribution		X					X		X			
VRx-3996/valganciclovir return							X				X	
VRx-3996/valganciclovir compliance assessment		X	X	X	X	X	X	X	X	X		
Survival and follow-up assessment and disease status												X

Study assessments may be performed ± 3 days of the recommended date (however the DLT assessment period should include a full 28 days). Study visits with PK assessments should occur on days that the patient will take both study drugs, VRx-3996 and valganciclovir. End of Treatment (ET) Visit assessments (if needed) will be the same as for the Safety Follow-Up Visit. Safety Follow-Up Visit will be performed 28 ± 7 days after last dose.

SR – Screening (within 21 days of Cycle 1 Day 1)

ET – End of Treatment

ST – Safety follow-up

SV – Survival follow-up contact (performed at least every 3 months after safety follow-up assessment)

X – Required

[X] – Biopsy tissue samples taken per standard of care during study participation and samples taken at the time of relapse should be submitted to the central pathology lab for review.

Informed consent – Informed consent may be performed at any time prior to the start of screening procedures.

EBER/histology Sample – Histology sample, indicative of current disease, to be sent to central pathology lab at the time of screening. Central pathology review/results not required for enrollment. Pathology review will include detection of EBV gene products.

Medical history – Record all cancer-related history over the patient's lifetime and collect non-cancer related history for the 2 years prior to study entry. For transplant recipients (except auto-SCT), collect the following historical information on donors: HIV1, HIV2, hepatitis B surface Ag, hepatitis B surface Ab, hepatitis B core Ab, hepatitis C Ab, HSV-1 Ab, HSV-2 Ab, CMV Ab IgG, CMV Ab IgM, EBV IgG-VCA (viral capsid antigen).

Vital signs – Performed just prior to first dose of valganciclovir and VRx-3996, and in concert with (but prior to) PK draws on Cycle 1 Day 1. On other indicated visit days, perform vital signs once (prior to study drugs dosing if administered in clinic). Vital signs include weight (in pounds), heart rate, respiratory rate, blood pressure, temperature, and oxygen saturation by pulse oximeter. Note that weight only needs to be recorded once daily.

Performance status – Either ECOG or KPS (See [Table 16](#) in the Appendix for conversion table).

Concomitant medications – Recorded from 28 days prior to Cycle 1 Day 1 to 28 days after last dose of study drugs, except for concomitant medications related to cancer treatment, for which lifetime history prior to entering the study will be recorded.

Urinalysis – [Urine] Color, appearance, glucose, bilirubin, ketone, specific gravity, blood, pH, protein, urobilinogen, nitrite, leukocyte esterase, RBC, WBC, epithelial cells.

Hematology - [Blood] Complete blood count with differential to include WBC, RBC, HGB, HCT, platelets, MCV, MCH and differential.

Chemistry - [Blood] Sodium, potassium, chloride, bicarbonate, blood urea nitrogen, creatinine, glucose, calcium, phosphate, magnesium, AST, ALT, total bilirubin, alkaline phosphatase, total protein, albumin, uric acid, and LDH.

Coagulation – [Blood] PT, PTT, and INR.

Serum pregnancy test – Only required for females of child-bearing potential.

Urine pregnancy test – Only required for females of child-bearing potential at the beginning of every cycle.

12-lead ECG – Careful skin preparation should be done to assure high quality ECGs and all ECGs should be collected on the same ECG machines. ECGs should be performed in as calm an environment as possible and not immediately following stressful procedures (i.e., biopsies, etc.) and distractions should be minimized, such as talking, TV, etc. Prior to each ECG, the patient should lie in a supine position in a calm environment for at least 5 minutes. When performed in triplicate, the ECGs should be performed ~1 minute apart. ECGs should be conducted prior to and as close to PK blood draws when timepoints coincide, followed by vital signs, when all 3 assessments are scheduled for the same time (in order: ECG, vital signs, then blood draw).

ECGs should be performed in triplicate at the following times:

- Screening
- Cycle 1 Day 1 pre-dose, and post-dose at 0.5 hr, 1 hr, 2 hr, 4 hr, and 6 hr
- Cycle 1 Day 2 pre-dose and post-dose at 2 hr
- Cycle 1 Day 15 pre-dose and post-dose at 2 hr
- Cycle 2 Day 1 pre-dose and post dose at 0.5 hr, 1 hr, 2 hr, 4 hr, and 6 hr
- Cycle 2 Day 15 pre-dose and post dose at 2 hr

Average corrected QT interval using Fridericia's method (QTcF) to be calculated to confirm eligibility.

At times not listed above, single ECGs should be performed. When performed on days that include PK draws, a single ECG should be performed as close as possible to each PK draw. For days when there are no scheduled PK draws, the ECG can be performed at any time during the clinic visit, irrespective of the time of study drug dosing. On study days requiring a single ECG, if ECG indicates an increased QTcF interval (i.e., >450 msec), 2 additional ECGs should be performed at least 2 minutes apart.

Head CT/MRI – Performed to rule out occult CNS disease prior to study entry.

Disease assessment – Performed at least every 2 cycles with initial assessment after Cycle 2 (may be adjusted based on Investigator discretion following discussion with Medical Monitor). Disease assessment performed using a modality appropriate for the patient's tumor (e.g., PET-CT scan, CT scans, MRI). Use a consistent modality for the same patient throughout the study. May include assessment of bone marrow (e.g., aspirate, biopsy) with cytogenetics and/or fluorescence in situ hybridization (FISH) as indicated. Disease assessment data including actual scan data and radiology reports will be submitted to the Sponsor as it becomes available for evaluation by a central radiologist reader. Investigator assessment of clinical response will be documented in the source and in Electronic Data Capture. When available, tumor tissue collected during the study should be provided to the central pathology lab.

PK sample(s) – [Blood] Collected for both valganciclovir and VRx-3996. Timepoints per [Section 6.4.1](#). Collection procedure outlined in the Study Manual for all sites. Study visits with PK assessments should occur on days that the patient will take both study drugs, VRx-3996 and valganciclovir.

Urine PK collections – At selected sites only urine will be collected for levels of VRx-3996 and its metabolites on Cycle 1 Day 1. Patients will be instructed to void urine prior to administration of study drug, then all urine will be collected as described in [Table 14](#) depending on the patient Cohort. Detailed instructions are included in the Study Manual.

Hepatitis B antigen/antibodies – [Blood] Includes surface antigen, core antibody, and surface antibody. Collection procedure outlined in the Study Manual.

Hepatitis B DNA PCR – [Blood] Collected on patients with positive hepatitis B core Ab or surface Ag.

Hepatitis C antibodies – [Blood] Collection procedure outlined in Study Manual. Any patient positive for hepatitis C Ab will be evaluated for hepatitis C circulating virus by qPCR.

Hepatitis C qPCR – [Blood] Required only for patients with evidence of hepatitis C based on serology.

Human leukocyte antigen (HLA) testing – [Blood] Determination of HLA class I and II. Collection procedure outlined in the Study Manual.

Exploratory biomarkers:

- Histone H3 acetylation*** – [Blood] Evaluates acetylation on PBMCs. Samples collected prior to administration of study drugs on Cycle 1 Day 1 (baseline), Cycle 1 Day 2, Cycle 1 Day 8. Collection procedure outlined in the Study Manual.
- Immune profile*** – [Blood] Evaluates immunophenotype and immune function in PBMCs. Samples are collected prior to administration of study drugs on Cycle 1 Day 1 (baseline), Cycle 1 Day 15, Cycle 2 Day 1, Cycle 3 Day 1, Cycle 4 Day 1, and ET. Collection procedure outlined in the Study Manual.
- EBV and CMV qPCR*** – [Blood] Collected prior to administration of study drugs on Cycle 1 Day 1 (baseline), Cycle 1 Days 2, 8, 15, 22, and Cycles 2–12 Day 1. Collection procedures are outlined in the Study Manual.

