9. ASSESSMENT OF SAFETY

9.1. Specification of Safety Parameters

9.1.1. Adverse Event (AE) Definition

An AE is any untoward medical event that occurs to a patient following the start of investigational product (IP) administration, whether the event is considered IP-related or not.

Pre-existing conditions are not considered an AE unless the condition worsens by at least 1 grade following the start of IP administration.

Adverse events will be captured with the first dose of study drugs (on Cycle 1 Day 1) and continue until 28 days after the last dose of study drugs or until a new anticancer treatment is started.

Death considered related to disease progression will not be considered an AE. However, all deaths within 28 days of last study drug administration or assessed as related to study drug, must be reported on a serious adverse event (SAE) form within 24 hours.

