9.3. Time Period for AE Reporting

Adverse Events will be recorded that occur following the first administration of study drugs (on Cycle 1 Day 1) up to and including 28 days after the last dose of study drugs or until the start of a new anticancer therapy.

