3.4.1.1 Primary Safety Endpoints

An AE is any untoward medical event that occurs in a patient following the start of investigational product (IP) administration, whether the event is considered IP-related or not. Pre-existing conditions are not considered an AE unless the condition worsens by at least 1 grade following the start of IP administration. Adverse events will be captured with the first dose of study drugs (on Cycle 1 Day 1) and continue until 28 days after the last dose of study drugs or until a new anticancer treatment is started whichever is first.

Dose-limiting toxicity AEs must meet all of the following criteria:

- Occurs during the first cycle (28 days) of study drug administration in Phase 1b only
- Is not incontrovertibly related to underlying disease
- In addition, to be considered a DLT, the AE will meet at least one of the criteria listed below:
 - Grade 4 anemia unexplained by underlying disease
 - Grade 4 febrile neutropenia
 - Grade 4 neutropenia lasting >5 days
 - Any other Grade 4 hematologic toxicity (thrombocytopenia, neutropenia, febrile neutropenia, anemia) of any duration
 - Grade 4 or higher tumor lysis syndrome
 - Grade 3 or higher thrombocytopenia (with or without bleeding)
 - Any requirement for platelet transfusion
 - Grade 3 or higher non-hematologic toxicity despite adequate supportive care
 - Results in a dose hold of >7 consecutive days

AEs that persist <72 hours and are able to be managed with supportive care may be excluded.

3.4.1.2 *Secondary Safety Endpoints*

Laboratory Parameters

Clinical laboratory evaluations will follow those outlined in the clinical study protocol and will be performed using a central or local laboratory. Evaluations include hematology, chemistry, urinalysis, coagulation, and pregnancy tests (for women of childbearing-potential only). Specific parameters to be collected are listed below:

- Hematology (blood): Complete blood count with differential to include white blood cells and differential, red blood cells, hemoglobin, hematocrit, platelets, mean corpuscular hemoglobin, mean corpuscular volume
- Chemistry (blood): Sodium, potassium, chloride, bicarbonate, blood urea nitrogen, creatinine, glucose, calcium, phosphate, magnesium, aspartate aminotransferase (AST), aminotransferase, alanine aminotransferase (ALT), total bilirubin, alkaline phosphatase, total protein, albumin, uric acid, and lactate dehydrogenase

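### The last scheduled adverse-event enquiry may take place up to 7 days before the 28-day post-treatment recording period ends, and no later contact covers those days

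*Protocol*

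**What the plan says.** **How long AEs are recorded.** Protocol Section 9.3 has AEs recorded "up to and including 28 days after the last dose of study drugs or until the start of a new anticancer therapy". Section 9.1.1 gives the same period ("continue until 28 days after the last dose of study drugs or until a new anticancer treatment is started"), and so does SAP Section 3.4.1.1 ("until 28 days after the last dose of study drugs or until a new anticancer treatment is started whichever is first"). Section 11.1 applies the Section 9.3 period to SAEs. Section 3.11 and the notes to Table 15 also take concomitant medications to 28 days after the last dose.

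**When the closing visit may take place.** Section 6.3.2 places the Safety Follow-Up Visit "approximately 28 days following the final administration of VRx-3996/valganciclovir". The footnote to Table 15 sets the window: "Safety Follow-Up Visit will be performed 28 ± 7 days after last dose".

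**What comes after it.** In Table 15 the rows for adverse events, concomitant medications, hematology and chemistry are marked up to and including the safety follow-up column and are blank in the survival column. Section 6.3.3 gives the content of the later contacts: "Survival and follow-up assessment will be conducted at least every 3 months for assessment of additional therapy, response status, and survival". These contacts may be done by record review, and AEs are not among the listed items.

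**A related safeguard.** The same footnote lets study assessments move by 3 days either way, but adds that the DLT assessment period must still cover 28 full days. There is no matching condition for the 28 days after treatment.

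**The concern.** The duty to record runs to Day 28, but the schedule need not support it. A site can hold the visit on Day 21, inside its window, and the protocol then prompts no further AE enquiry for Days 22 to 28. An event in those days is recorded only if the patient volunteers it, if it leads to an unscheduled contact, or if it turns up in the records.

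Safety and tolerability is a primary objective, and the SAP reports it as patient incidence of treatment-emergent AEs (Section 4.5.2). If new events are missed, incidence can only be understated. The length of active ascertainment would also differ between patients, from 21 to 28 days after the last dose. The SAP plans no summary of how far AE follow-up extended after treatment, so a shortfall would not be visible in the incidence tables.

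**Working it through.** The documents give no figure for this gap, so there is nothing to reproduce. The check is interval arithmetic.

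**Inputs**
- End of AE recording: W = 28 days after the last dose (Protocol 9.1.1 and 9.3; SAP 3.4.1.1), for a patient who has not started new anticancer therapy.
- Permitted visit day: V = 21, 22, …, 35, which is 15 days (Table 15 footnote, 28 ± 7).
- Next scheduled contact: survival follow-up, with no AE mark (Table 15; Section 6.3.3).

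**Formula.** Days without a scheduled AE enquiry = max(0, W − V). Share of the period = max(0, 28 − V) / 28.

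| Visit day V | Gap (days) | Share of 28 days |
|---|---|---|
| 21 | 7 | 25.0% |
| 22 | 6 | 21.4% |
| 23 | 5 | 17.9% |
| 24 | 4 | 14.3% |
| 25 | 3 | 10.7% |
| 26 | 2 | 7.1% |
| 27 | 1 | 3.6% |
| 28 to 35 | 0 | 0% |

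**Maximum.** 7 / 28 = 25.0%, reached only by a visit on Day 21.

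**Permitted days that leave a gap.** 7 of 15 = 46.7%.

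**Mean gap.** The documents give no distribution of visit days. If they were spread evenly over Days 21 to 35 (assumption), the mean gap would be (7 + 6 + 5 + 4 + 3 + 2 + 1) / 15 = 28 / 15 = 1.87 days, and 1.87 / 28 = 6.7%. The possible range of the mean is wide: 0 days if every visit is on or after Day 28, and 7 days if every visit is on Day 21.

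**After the change.** With V restricted to 28 to 35, max(0, 28 − V) = 0 for every permitted day, so the maximum gap falls from 7 days to 0.

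**The case against.** A reader might infer that up to a quarter of the post-treatment period is unobserved. The documents do not support that. The recording duty is set by calendar, so a site that stops recording on Day 21 breaches Section 9.3. Laboratory abnormalities that qualify as AEs are followed until they return to normal or are explained, with twice-weekly assessment when toxicity is the cause (Section 9.1.2). Unscheduled visits are entered in the database (Section 6.3.4). The SAP's treatment-emergent definition has no upper limit tied to the safety visit (Section 4.5.2), so an event learned of later can still be counted. What is missing is a scheduled enquiry. That part stands, because following known abnormalities does not find new ones and no unscheduled contact is required.

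A reader might also infer that deaths within 28 days would be undercounted. This does not hold. Section 9.1.1 states that "all deaths within 28 days of last study drug administration or assessed as related to study drug, must be reported"; survival is followed after the safety visit; overall survival needs a date of death; and SAP Section 4.5.3 lists all deaths, including those in post-treatment follow-up. A death on Day 25 would normally be dated and counted unless follow-up was lost or withdrawn.

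Nor does an SAE discovered late break the 24-hour rule. Section 11.1 starts that clock when the investigator becomes aware. The remaining point is only that awareness may itself come late.

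Four further arguments limit the importance of the point:
- The visit target is about Day 28. If visits cluster there, the mean gap is below the even-spread figure.
- AE capture ends when new anticancer therapy starts, which shortens or removes the gap for some of the patients who stop for progression.
- Safety is summarised descriptively with no formal comparison of cohorts (SAP 4.1.1), and the DLT period is protected, so the choice of Phase 2 dose does not depend on this.
- Section 1.8 reports a median half-life of 1.8 hours for VRx-3996 (range 1.1 to 7.8), so events after Day 21 may say less about that drug. The protocol nevertheless chose 28 days for the combination, and its schedule should deliver that period.

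Finally, SAP Sections 3.4 and 4.9 describe some conduct in the past tense. For patients whose safety visit is already over, a new window changes nothing.

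**Conclusion.** The mismatch is real and small. AEs and concomitant medications are due through Day 28, yet the last scheduled enquiry may be on Day 21 and the survival contacts do not fill the gap. The worst case is 7 of 28 days (25%) for a single patient. The mean of 1.9 days (6.7%) rests on the even-spread assumption and on every patient having the full 28-day period, so it is illustrative and not an estimate.

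The likely effect is some under-ascertainment of new non-serious AEs and new laboratory findings, with an occasional SAE coming to light late. Deaths, the response rate, the sample size and the DLT period are not materially affected. The change is worth making because it costs little and removes a possible downward bias in the summary of a primary objective.

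**What to change.** In Protocol Table 15 and Section 6.3.2, set the Safety Follow-Up Visit at 28 to 35 days after the last dose, or just before new anticancer therapy if that starts sooner. Alternatively, keep the present window and require, whenever the visit takes place before Day 28, a telephone contact on or after Day 28 that asks about AEs, SAEs and concomitant medications.

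The cost is a change of wording in two places, slightly less flexibility in booking the visit, and an occasional call. No analysis method changes. For patients whose visit has already taken place, the clinical study report could state how many were seen before Day 28, so that the reader can judge the size of any shortfall.
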